Systolic blood pressure of 160 mm Hg or more, or diastolic blood pressure of 110 mm Hg or more on two occasions at least 4 hours apart (unless antihypertensive therapy is initiated before this time), Thrombocytopenia (platelet count less than $100,000 * 10^9/L$), Impaired liver function as indicated by abnormally elevated blood concentrations of liver enzymes (to twice the upper limit normal concentration), and severe persistent right upper quadrant or epigastric pain unresponsive to medication and not accounted for by alternative diagnoses, Renal insufficiency (serum creatinine concentration more than 1.1 mg/dL or a doubling of the serum creatinine concentration in the absence of other renal disease), Pulmonary edema
 New-onset headache unresponsive to medication and not accounted for by alternative diagnoses, Visual disturbances

Study population:

Patient characteristics:

Participants who will be included in this study are pregnant women who are at high risk for developing pre-eclampsia as defined by the ACOG practice bulletin (for review (67)).

Inclusion criteria:

To be eligible to be included in the study, a woman has to have all of the following; Confirmed y, gestational age $< 12^{+0}$ weeks, live fetus at time of booking ultrasound scan

(between 11⁺⁰ and 13⁺⁶ weeks of gestation), and to be considered as high risk of preeclampsia. According to ACOG (67), pregnant women are considered high risk of preeclampsia if they showed at least one of the following; History of preeclampsia, especially when accompanied by an adverse outcome, Multifetal gestation, chronic hypertension, Type 1 or 2 diabetes, Renal disease, Autoimmune disease (ie, systemic lupus erythematosus, the antiphospholipid syndrome), OR more than one of the following: Nulliparity, Obesity (body mass index greater than 30), Family history of preeclampsia (mother or sister), Sociodemographic characteristics (African American race, low socioeconomic status), Age 35 years or older, Personal history factors (eg, low birth weight or small for gestational age, previous adverse pregnancy outcome, more than 10-year pregnancy interval)

Exclusion criteria:

Age under 18 years, hyperemesis gravidarum, unable to sign the consent form, type 1 or 2 diabetes mellitus, early gestational diabetes, auto-immune disease, fetal abnormality identified at time of scanning (between 11⁺⁰ and 13⁺⁶ weeks of gestation), bleeding disorder, peptic ulcer, hypersensitivity to aspirin or metformin, long use of NSAIDS before initiation of intervention, contraindication to metformin or aspirin and participation in another concurrent trial.

Study sites:

The study will be conducted at the Women Wellness and Research Center (WWRC), Doha, Qatar. Patient will be identified from three Primary Health Centers. There will, however, will be very few volunteers who will have all their visits and tests done at the WWRC with the health center facilitating their identification only.

Study methods:

Patient identification and randomization

If the primary physician in the Primary Health Center or the main center identifies a potential candidate for the study based on the inclusion and exclusion criteria, he/she will inform the patient about the study and document her willingness to participate in the study in the electronic medical record to avoid cold calling and according to HIPAA recommendations. The investigator of the respective site will then be contacted through email by the primary physician.

the patient will be contacted by the study investigator and arrange an appointment in the WWRC to inform her about the study and if she accepted to participate, give her the patient information leaflet (PIL) and then obtain informed consent once all her questions have been answered.

Each center has one coordinator, who will be responsible in conjunction with the investigator for recruitment, clinical interviews, determining eligibility and obtaining signed informed consent forms. After successful screening, eligible pregnant women will be randomly assigned to either intervention or control group. Random sized blocks of 4 or 6 will be computer generated with 1:2 ratio.

Sample isolation and laboratory studies (appendix 2):

Blood samples, 5 ml maternal venous whole blood will be collected by a laboratory phlebotomist or a nurse at each study visit (one at baseline, and one at each following trimester/visit and admission/s, see appendix 2) for all included subjects. The blood will be collected in vacutainer tubes without additives and will be allowed to clot for 30 min at room temperature before centrifugation for 15 min at 1000 x g. The supernatant (serum) will be labelled with research mark and the patient study number and stored at -20C until ELISA is performed. Serum levels of sFlt-1, free VEGF and free PIGF will be tested using ELISA. The study coordinators will collect and transfer the samples daily to the research laboratory at Sidra Medicine were further analysis to be carried out. Kits for ELISA will be purchased from R&D. Patient confidentiality will be maintained during this process. **Placenta samples**: Two random 2x2cm whole thickness placenta biopsies will be taken from 2cm from the cord insertion (from opposite sites) will be collected immediately after the delivery on the labor room or in the operating theatre by the nurse. These samples will be washed and flash-frozen and transported to Sidra Medicine for storage for future analysis to study the association between maternal and fetal DNA mutations (targeted genome sequencing Flt-1 region) and mRNA expression level (targeted) and development of PET.

To further our understanding of gene regulation of metformin effects in pre-eclampsia we will use a high frequency immune monitoring targeted transcriptome finger printing assay (TFA) including a high-throughput qPCR platform (68,69). This assay relies on gene sets, so called transcriptional modules, which had previously been identified by comprehensive network analysis on the basis of gene co-expression in whole blood samples of nearly 1000 subjects across 16 immunological conditions. Of these transcriptional modules, 273 target genes were selected, representing 66 functionally annotated modules, with 4 representative genes per module. This allows high frequency monitoring of the entire modular transcriptional repertoire in a cost effective way. In brief, small volumes of blood (around 50 µl) from each blood sample will be transferred into a microfuge tube containing twice the blood volume of tempus solution from the following groups of pregnant women: A) PET high risk, B) PET receiving standard treatment and C) PET receiving metformin. The sample will be mixed to disrupt cells and release the RNA. Samples will be stored at -20 C. Once all samples for the study are collected, RNA will be isolated (using the Tempus Spin RNA isolation kit from Invitrogen) and cDNA synthesized using standard protocol. The following qPCR, using primer pairs to amplify 4 representative genes per module, will be performed on the Fluidigm platform (Sidra core ~~facilities~~ ^{appendix 3} for number of patient in this analysis)

We will collect and store samples for future determination of the association between maternal and fetal DNA mutations (targeted genome sequencing Flt-1 region) and mRNA expression level (targeted) and development of PET.

Risk minimization strategy:

Loss of confidentiality:

There is a minimal risk of confidentiality loss. To minimize this risk, data will be entered in to a clinical trial management software. The software will be secured with user name and password for study investigators and only accessible by them. Data extraction will only be accessible to study PIs and co-PIs. Paper based data collection sheet will be secured in locked cabinets accessible only by study PIs and co-PIs. Only de-identified data will be shared amongst investigators and Data and Safety Monitoring Committee (DSMC). If a breach in confidentiality occurs, the IRB will be notified immediately.

Linking information between collected data and patient's identifiable information will be stored in a locked cabinet and/or PI password locked computer. Information on the password protected computer database will only be accessed by the investigators. Furthermore, the PI's office will remain locked. All study documentation will be stored according to the MRC and GCP guideline.

Data and Safety Monitoring Committee (DSMC)

A DSMC of this trial consisting of [name] (senior consultant, WWRC), [name] (Sr. Consultant Ob/Gyn department), [name] (Senior Consultant at WWRC), [name] (Senior consultant at Sidra Medicine), [name] [name] (Director of Pharmacy, NCCCR) and [name] (Senior Consultant Clinical Biochemist at Sidra) will be set up. These are all very skilled clinical research and ethical matters and independent of the research. The committee will meet every three months to review (a) the conduct of the trial, (b) recruitment and progress, (c) randomization and (d) data collection.

Any adverse event (SAE) will be reviewed by the DSMC. Unanticipated SAEs will be reported to the DSMB within 48 hours (expedited reporting); the study Co-PIs will be responsible for reporting any unanticipated SAEs to the DSMC and the MRC.

A SAEs will be deemed Unanticipated if it is related to the study intervention. Other SAEs will be reported to the DSMC in the regular safety update. Accordingly, if required the DSMB may request follow up information and recommend continuation, modification (study protocol or consent), or termination of the study.

Study procedure:

Screening and enrollment:

ian - Revised On May 2017

Page 11 of 22

Initial screening: The study will take place at the Women Hospital. All clinical care providers at participating centers will be briefed about the study. Pregnant women presenting at their first antenatal visit (< 12⁺ weeks of gestation) will be screened by their primary physician for risk of pre-eclampsia. To avoid cold calling, a pregnant woman deemed high risk for pre-eclampsia will be informed about the study by her primary physician. If she expressed an interest in study participation, that will be documented by the primary physician in her medical record. She will be instructed to contact the study investigators directly or permit to share her information with study team to be contacted by a trained study team member to explain the study in detail, and then obtain a written informed consent (appendix 4).

Randomization and initiation of the study:

Once recruited, the patient data will be entered onto a web-based randomization software to determine study group and to the clinical trial management software, where a study ID number will be assigned. If the patient agrees to enter the trial, the site coordinator will contact the study physician to initiate study protocol (appendix 2) and then the patient will continue to be followed-up by her clinical team. In cases where patient assigned to control group and diagnosed with GDM and started on metformin, she will be moved to intervention group and analyzed as late started. If patient declined to participate initially, or dropped out from the study, all her data will be removed.

A clinical trial management software will be utilized to enter patient data. Each study Co-PI (physician) will lead a study site and supported by study coordinator. They will be responsible for reviewing patient eligibility, initiating the study protocol and patient counselling. They will meet regularly to share study updates. Study coordinators will be responsible for patient counselling, obtaining written informed consent, data collection and entry, and blood samples and placenta shipment from the study sites to study research laboratory at Sidra Medicine. The LPI will meet with the research team monthly to review various aspects of the trial to ensure conformation to the protocol and principles of GCP.

Collected data (appendix 5):

Variables to be collected include patient demographic characteristics, past medical and surgical history, past medication history, allergies, vital signs, CBC as routinely done and LFT, serum creatinine and biomarker serum level (sFlt-1, VEGF, PIGF). Blood samples will be collected by the phlebotomist or the responsible nurse. The blood investigations, 5 ml blood sample will be collected at baseline, second and third trimester and after delivery. The blood sample will be used for CBC, LFT, serum creatinine, and study serum biomarker in aim 2 (sFLT-1, VEGF, PIGF), and well as for storage for future DNA/RNA analysis for aim 3. Further, placenta samples will be collected and stored for future DNA/RNA analysis.

Medication adherence and adverse drug related events (ADRs):

Medication adherence is crucial to achieve the study objectives. Patient medication adherence is measured using the pill count method on each visit and Morisky scale (appendix 6) in

1st - Revised On May 2017

Page 12 of 22

each visit or telephone call. Furthermore, to increase patient medication adherence, a reminder SMS will be send as well as three telephone calls to individual patient on regular basis. Adverse drug reaction (ADRs) will be reported using [name] Medical Corporation ADR form (Appendix 7) to both DSMC and MRC when they occur, however, serious ADRs will be reported within 48 hours by the study PI.

6. Sample size and calculation

Our sample size calculation was based on Syngelaki A. et al. (2016) findings. In this study, obese patient where either randomized to metformin or placebo to see the effect on neonatal birth weight. As a secondary outcome, metformin use was associated with 76% reduction in PET (3% versus 11.3% respectively, OR 0.24, 95% CI 0.10 – 0.61, $P = 0.001$).

We expect that for a study power of 80% and to detect a reduction at a level of 5% significance, with considering above outcome estimates it is approximately estimated to be 172 patients in each arm, for a total of 344 in both group based on 1:1 ratio. Allowing for a maximum 20% dropout, we estimate that 414 patients would need to undergo randomization, to give 207 patients in each group.

7. Data collection methods and procedure

These will be at baseline, in the second and again in the third trimesters. The data to be collected include patient clinical information, blood sample and placental tissue (appendix 5). At each study visit 5 ml maternal venous whole blood will be collected by a laboratory phlebotomist or a nurse (one at baseline, and one at each following trimester/visit and admission/s, see appendix 2) for all included subjects. The blood sample will be used for measuring blood markers for aim 2 and stored for future DNA/RNA analysis for aim 3. In addition, placental tissue will be collected and stored for future DNA/RNA analysis. In brief:

- (a) Baseline Data (Week 11⁺⁰ to 13⁺⁶): Patient sociodemographic data including age and ethnicity, Obstetrical, medical, surgical and medication history, current pregnancy information, CBC, as routinely done and study biomarkers of LFT, serum creatinine, sFlt-1, VEGF and PIGF.
- (b) Second (week 19⁺⁰ to 24⁺⁶) and third trimester visits (week 32⁺⁰ to 34⁺⁶): At these visits the same data collected at baseline will be obtained. If the patient is, however, admitted for pre-eclampsia before the third visit, the collection will follow the pre-eclampsia diagnosis at admission including treatment offered, length of hospitalization and management.
- (c) At delivery data to be collected will include gestational age at admission, vital signs, indication for delivery, type of delivery, compliance with protocol, blood for CBC, LFT, and the biomarkers of interest. Post-delivery, discharge vitals, antihypertensive treatment on discharge will be collected.

(d) Exit interview: patient will be called to check for any relevant ADR.

8. Data Management and Analysis plan

Data management:

Upon randomization, research coordinators will be responsible for data collection using approved CRFs. To maintain patient confidentiality, study document such as signed informed consent, and CRFs will be stored in locked cabinets, excel file containing patient identifiable information will be password protected, and all data including patient clinical information and research laboratory results will be entered into the clinical trial management software using patient generated study ID number.

Data analysis:

Descriptive data: Numerical data will be presented as mean and standard deviation where normally distributed or median and range where it's not normally distributed. Categorical data will be presented as frequency and percentages. The percentage of women developed PET will be compared between the intervention and control group using chi square test.

Quantitative data between two arms will be analyzed using either "Unpaired t test or Mann Whitney U test depending on normality of the data distribution". Also, outcomes measured at different time points should be statistically analyzed both within and between groups using repeated measure ANOVA statistical method followed by appropriate multiple comparison tests. All P values presented will be two-tailed. A multivariate logistic regression will be employed to assess the association between metformin use and PET adjusting for confounding factors such as patient demographics (age, GA at delivery, history of risk factors of PET\mentioned above) and co-morbidities such as DM, the dose of metformin, the need to use of antihypertensive drugs, including duration of treatment and any other medications. P values <0.05 will be considered as statistically significant. All Statistical analyses will be done using statistical packages SPSS 22.0 (SPSS Inc. Chicago, IL) and Epi-info (Centers for Disease Control and Prevention, Atlanta, GA) software.

9. Anticipated results and evaluation criteria

As an open label study, we hope the results of this study will generate robust data that will be used to inform the design equipped to design of a larger national study. Moreover, based on the findings of previous published literature, we predict that expression of sFlt-1, VEGF and PIGF will be significantly altered in pre-eclamptic patients. The design of this study will help determine and validate the clinical utility of the aforementioned biomarker in routine practice for the prediction of PET and disease severity. The use of metformin is expected to reduce the anticipated effects of sFlt-1 as an antiangiogenic factor, therefore, reducing the incidence of

PET and indeed improving maternal and neonatal outcomes and quality of life, reducing hospital admissions and cost of care and better utilization of health care system resources.

This collaborative study involves investigators (scientists and clinicians) from the PHCC, HGH, Women's Hospital [name] and Sidra. Such a cross-disciplinary approach will provide an opportunity for training future scientist in the field of women's health. The more junior members of the team will have the opportunity to be trained on translational research design, and clinical trial management and thereby enhancing the research capacity which both are aligned with Qatar national health strategy. The women hospital will be better catered with enhanced research skills. Pregnant women are usually excluded from clinical trial; however, an advantage of this trial is the safety the intervention (metformin) and thereby increasing public engagement with research and awareness of its importance and benefits.

Evaluation criteria for this study are patient recruitment, quality and consistency of the data and safety of the intervention. Further, the percentage women who developed PET in each arm as well as changes in the studied biomarkers will be quantified and accepting the null hypothesis.

10. Plans for disseminating research results

Once the project is funded, the study team will initiate monthly meetings to discuss study plans and patient recruitment. Team leaders will also meet monthly to share study updates. Furthermore, the study results will be shared among peers in the department through presentation of study findings. Finally, once the study is completed we aim to present our finding at the [name] Medical Corporation Annual Research Day, local and international conferences and in peer-reviewed journals.

11. Future plans

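### The randomisation instruction is 1:2 in blocks of 4 or 6, which a block of 4 cannot hold, while the sample size assumes 1:1 with 207 women per group

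*SAP*

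**What the plan says.** Section 5, under patient identification and randomisation, gives the allocation rule: "Random sized blocks of 4 or 6 will be computer generated with 1:2 ratio". It does not say which arm takes the larger share.

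Section 6 sizes the trial on the other ratio: "approximately estimated to be 172 patients in each arm, for a total of 344 in both group based on 1:1 ratio". The inputs are an earlier trial in obese women, in which "metformin use was associated with 76% reduction in PET (3% versus 11.3% respectively", and a design "for a study power of 80% and to detect a reduction at a level of 5% significance". It then inflates for loss: "Allowing for a maximum 20% dropout, we estimate that 414 patients would need to undergo randomization, to give 207 patients in each group".

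Two other places bear on the point. Under randomisation and initiation of the study: "If patient declined to participate initially, or dropped out from the study, all her data will be removed". In Section 8, the analysis of pre-eclampsia (PET): "The percentage of women developed PET will be compared between the intervention and control group using chi square test", with two-tailed P values and no mention of a continuity correction.

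**The concern.** The allocation ratio is a defining design parameter, and allocation is handed to web-based software that must be given a single ratio. The document gives two. The one placed next to the block sizes cannot be carried out in one of those block sizes.

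If the software were set to 1:2 in blocks of 6 only, the arm sizes would not be those behind the sample size. Between 138 and 276 women would receive metformin instead of 207, and power would depend on a choice of larger arm that is nowhere stated.

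The dropout inflation is a separate, smaller matter. If 20% of women are lost, 414 does not leave the 344 that the calculation requires.

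**Working it through.** **Inputs.** PET rates of 3% (metformin) and 11.3% (control), 80% power, 5% significance, 172 evaluable and 207 randomised per group, 20% dropout (all Section 6); two-tailed chi-square test (Section 8); ratio and block sizes (Section 5). One assumption is mine: dropout is equal in both arms.

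**Reproducing 172.** The usual two-proportion formula with pooled variance under the null gives 151 per arm. With a continuity correction it gives 174, close to the stated 172. The SAP names no formula, so the corrected version is the likely source but not a certain one.

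**Blocks.**

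| Ratio | Block of 4 | Block of 6 |
|---|---|---|
| 1:1 | 2 + 2 | 3 + 3 |
| 1:2 | 1.33 + 2.67, impossible | 2 + 4 |

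**Arm sizes.** 414/3 = 138, so 1:2 gives 138 and 276, against 207 and 207 in Section 6. After 20% loss, 414 × 0.8 = 331.2. That is about 166 per arm at 1:1, or about 110 and 221 at 1:2.

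**Dropout.** 172 × 1.2 = 206.4, rounded up to 207, so 20% was added on. To keep 172 after losing 20% takes 172/0.8 = 215 per arm, 430 in total. What 414 covers is 1 − 344/414 = 16.9%.

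**Power.** Exact power was found by enumerating every pair of binomial outcomes at 3% and 11.3% and summing the probability of those with a chi-square above 3.841. Because the SAP does not say whether a continuity correction applies, both versions are shown.

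| Scenario | Metformin / control | Uncorrected | Yates |
|---|---|---|---|
| No dropout, 1:1 | 207 / 207 | 92.5% | 89.8% |
| No dropout, 1:2 | 138 / 276 | 87.9% | 82.8% |
| No dropout, 2:1 | 276 / 138 | 91.3% | 87.0% |
| Planned evaluable number, 1:1 | 172 / 172 | 87.4% | 82.5% |
| Planned evaluable number, 1:2 | 115 / 229 | 80.2% | 72.4% |
| Planned evaluable number, 2:1 | 229 / 115 | 86.1% | 79.5% |
| 414 less 20%, 1:1 | 166 / 166 | 86.0% | 80.8% |
| 414 less 20%, 1:2 | 110 / 221 | 78.9% | 70.1% |
| 414 less 20%, 2:1 | 221 / 110 | 84.3% | 78.9% |

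At 20% loss, moving from 1:1 to unequal allocation costs 86.0 − 78.9 = 7.1 points uncorrected, or 80.8 − 70.1 = 10.7 with Yates, if metformin is the smaller arm. If control is the smaller arm, the cost is about 2 points on either version. The dropout slip alone (172 to 166 per arm at 1:1) costs 87.4 − 86.0 = 1.4 points uncorrected, or 82.5 − 80.8 = 1.7 with Yates.

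**Size if 1:2 were kept.** The continuity-corrected formula, the one closest to 172, needs 363 evaluable women (242 metformin, 121 control; 363/0.8, about 454 randomised) if metformin is the larger arm. It needs 413 (138 metformin, 275 control; 413/0.8, about 517 randomised) if control is.

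**The case against.** The strongest reply is that 1:2 is a slip and nobody intends a 1:2 trial. The sentence names no arms, both block sizes suit 1:1 exactly, and Section 6 gives 1:1, 172 per arm and 207 per group without ambiguity. This is the most plausible reading. It does not remove the defect, because the faulty sentence is the operative one for the randomisation list and the document offers no correction of it.

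The second reply is that the alarming power figures depend on several conditions at once: 1:2 is actually run, metformin is the smaller arm, the full 20% is lost (Section 6 calls this a maximum), and a continuity correction is used that the SAP never mentions. That is fair. At the planned 344 evaluable women, the uncorrected test still has 80.2% power in the less favourable 1:2 arrangement. The case for correction therefore rests on the contradiction and the unworkable block, not on the lowest power figure.

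The third reply is that the dropout error is harmless. On the uncorrected formula, 151 per arm is enough and 414 would absorb 1 − 302/414 = 27% loss. This also stands as far as power goes: at 1:1 with 20% loss the planned test keeps at least 80% on either version. The stated allowance is still wrong for the 344 the SAP itself requires. The intention-to-treat statement in Section 5 does not bring the lost women back, because the SAP elsewhere removes the data of those who drop out.

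**Conclusion.** The concern holds. Sections 5 and 6 give incompatible allocation ratios, and the Section 5 rule cannot be executed in blocks of 4. It must be corrected whatever was intended, although 1:1 is much the likelier intention.

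If 1:2 were run with 414 women and 20% were lost equally from both arms, the cost would be about 7 to 11 points of power with metformin as the smaller arm, taking power below 80% on either version of the test. With control as the smaller arm the cost is about 2 points. These figures rest on the planned rates of 3% and 11.3%.

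The dropout allowance is a minor error: 16.9% instead of 20%, under 2 points of power, and not enough by itself to miss the 80% target for the planned test.

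**What to change.** In Section 5, state that random blocks of 4 or 6 are generated with a 1:1 ratio, and check the randomisation list, or the software settings, against that.

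If 1:2 is truly intended, name the larger arm, use block sizes that are multiples of 3, and redo the arm sizes and power in Section 6 for that ratio.

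In Section 6, either say that 414 randomised (207 per group) allows for about 16.9% dropout, or say that 20% dropout leaves about 331 evaluable women, about 166 per group. Give the power for the chi-square test and name the method: for 166 per group, 86% exact without continuity correction or 81% exact with Yates' correction.

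The 1:1 repair costs wording and a check of the list, with no extra patients. Keeping 1:2 could cost more: on the continuity-corrected formula, about 454 or 517 women randomised instead of 414, depending on which arm is larger.

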Metformin has been in use since 1957 but its specific mechanism of action is unknown (62). Previously, AMPK-activation has been identified as one of the mechanisms by which it exerts its angiogenic activity (63). However, metformin does not activate AMPK directly. Instead, AMPK activation is a result of metformin inhibition of the mitochondrial respiratory chain complex 1 (reviewed in (64,65)). Apart from diabetes, it has also been implicated in the prevention of cancer, adverse outcomes in women with PCOS and most recently in the prevention of PET (reviewed in (66)). In an ex-vivo study using primary placental tissue from PET placentas, metformin treatment resulted in reduced endothelial dysfunction, enhanced vasodilatation and induced angiogenesis by sFlt-1 and endoglin reduction possibly at the mitochondrial level (30). Despite these, the exact mechanism behind its role in the prevention of PET remains poorly understood. Further clarification of how metformin decreases the incidence of pre-eclampsia needs to be examined. Here we plan to explore altered maternal serum levels of sFlt-1, PIGF and VEGF in pregnant women using metformin.

5. Study design and methodology

This is an open label, randomized control trial (RCT) in which high risk for pre-eclampsia pregnant subjects will be randomly assigned to either an intervention group (metformin 1 gm twice daily plus aspirin 100 mg per day and standard of care) versus control group (aspirin 100 mg per day and standard of care) that will be administered between 11^{+0} to 13^{+6} weeks of gestation until delivery (appendix 1). Only women at high risk of pre-eclampsia as defined by the ACOG practice bulletin will be included (see inclusion criteria). Patient assignment will not be blinded as control group will not be given a placebo; the data will be analyzed on an intention to treat basis. Enrolled subjects will be followed throughout pregnancy and up to 30 days post-delivery (as per hospital practice).

Study definitions:

High risk of preeclampsia:

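### Section 5 is unclear on whether a woman agrees to enter before or after open-label allocation, and it deletes the data of women who decline or drop out

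*SAP*

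**What the plan says.** The order of events is described in several places in Section 5 of the SAP.

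- **Study procedure, randomization and initiation of the study.** The first step is "Once recruited, the patient data will be entered onto a web-based randomization software to determine study group", and a study ID is assigned. The next sentence reads "If the patient agrees to enter the trial, the site coordinator will contact the study physician to initiate study protocol". Two sentences later comes "If patient declined to participate initially, or dropped out from the study, all her data will be removed".
- **Study methods, patient identification and randomization.** At the appointment the investigator is to "give her the patient information leaflet (PIL) and then obtain informed consent once all her questions have been answered". The coordinator's recruitment duties include eligibility and signed consent forms. Only then does the text say "After successful screening, eligible pregnant women will be randomly assigned to either intervention or control group".
- **Study procedure, screening and enrollment.** The primary physician screens for risk, the study is explained, and written consent is taken. This paragraph does not mention assignment, but it stands immediately before the randomization paragraph.
- **Study design and methodology.** "Patient assignment will not be blinded as control group will not be given a placebo; the data will be analyzed on an intention to treat".

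**The concern.** The randomization paragraph, taken in sentence order, puts a condition of agreement after the study group has been set. It then removes the data of anyone who declines or drops out. The other paragraphs put consent first. A site could therefore allocate, meet a refusal, and delete the woman.

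This matters because the trial is open label and only one arm adds a drug, for which Section 4 lists gastrointestinal side effects. Refusal after allocation could differ between arms. The women left would then no longer be the groups that were randomized. If their records are removed, an intention-to-treat analysis has nothing to analyze for them, and refusers cannot be compared with those who stayed.

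**Working it through.** **1. The sequence, side by side**

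| Step | Study methods; screening and enrollment | Randomization and initiation |
|---|---|---|
| 1 | Information given | Woman is described as recruited |
| 2 | Written consent | Software sets the study group; study ID given |
| 3 | Random assignment (study methods only) | Condition that she agrees; protocol started |
| 4 | – | Data removed if she declined at the start or dropped out |

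The right-hand column fits the left only if its step 3 repeats consent already given and if declining at the start means declining before step 2. Nothing in the randomization paragraph says so. Section 8 starts CRF data collection at randomization, so a woman who declined before that would have little study data to remove. That makes the benign reading less comfortable, but does not exclude it.

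The dropout half of the removal rule is firmer. Section 6 adds an allowance of up to 20% for dropout to reach the 414 women to be randomized, so the plan itself uses dropout for allocated women. At that maximum the rule would reach 0.20 × 414 ≈ 83 of them.

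**2. The plan's own sample size**

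Inputs from Section 6: 3% versus 11.3%, 80% power, 5% significance, 1:1. Section 8 makes tests two-tailed.

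The two-proportion formula gives n = [1.96·√(2 × 0.0715 × 0.9285) + 0.842·√(0.113 × 0.887 + 0.03 × 0.97)]² / 0.083² = 151 per arm, or 174 with continuity correction. The plan's 172 is reproduced to within 2 women. Its 207 is 172 × 1.2 = 206.4, rounded up.

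**3. What selective removal could do**

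Taken from the plan: p = 11.3% and 207 per arm. Assumed, with no support in the plan: no true effect; removal from the metformin arm only; a fraction f removed; and risk in those removed equal to k times the average.

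- Rate left in the metformin arm: p(1 − fk)/(1 − f).
- Rejection probability: Φ[(d − 1.96·se0)/se1] + Φ[(−d − 1.96·se0)/se1]. Here d is the apparent difference, se0 the pooled and se1 the unpooled standard error, with 207 against 207(1 − f) women.

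Example, f = 0.20 and k = 2:

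- Rate = 0.113 × 0.6/0.8 = 0.0848, so d = 0.0283.
- se0 = 0.0313 and se1 = 0.0309.
- Rejection = Φ(−1.07) + Φ(−2.91) = 0.141 + 0.002 = 0.143.

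| f | k | Rate left | Relative risk | Rejection at nominal 5% |
|---|---|---|---|---|
| 0.10 | 0.5 | 11.9% | 1.06 | 5.5% |
| 0.10 | 1 | 11.3% | 1.00 | 5.0% |
| 0.10 | 2 | 10.0% | 0.89 | 6.8% |
| 0.20 | 0.5 | 12.7% | 1.13 | 7.2% |
| 0.20 | 1 | 11.3% | 1.00 | 5.0% |
| 0.20 | 2 | 8.5% | 0.75 | 14.3% |

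In the last row the spurious difference is 11.3 − 8.5 = 2.8 points, about a third of the planned 11.3 − 3 = 8.3 points.

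**4. Is it loss of numbers?**

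No. If 20% of both arms were lost at random, power for the planned effect would still be about 84% by the uncorrected formula. The issue is selection.

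**The case against.** The strongest reply is that the plan already puts consent first. The allocation step applies to a woman who has been recruited. The study methods text counts signed consent among the recruitment duties, and the consent paragraph directly precedes the randomization paragraph. On that reading the later condition of agreement is a clumsy repetition, and "If patient declined to participate initially" describes a woman who never joined, whose data would ordinarily not be kept. Appendices cited for the design, study initiation and consent are not in the material at hand and may settle the order.

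Much of this stands. A reader might infer that women are told their arm and then choose whether to join. The SAP does not say that: it states that assignment is unblinded, not that the arm is disclosed before agreement. Nor does it say that the randomization software's allocation record is erased, and the monitoring committee reviews recruitment and randomization every three months. To claim that refusers leave no trace would go too far.

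The inputs to the illustration are also assumed. The plan's only 20% is a maximum for overall dropout, which is a different quantity from refusal at entry. Gastrointestinal effects arise on treatment, so they bear more on later dropout than on refusal at entry.

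What the reply does not remove is that the literal order permits refusal after allocation, and that the removal rule is not limited to women who have not been allocated.

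**Conclusion.** The point holds as an ambiguity and an internal conflict. The randomization paragraph can be followed in a way that contradicts the consent-first order elsewhere in Section 5. Combined with its data-removal rule, it would allow exclusion after allocation in an open-label trial declared to be analyzed by intention to treat. The removal of dropouts' data conflicts with that declaration even on the benign reading of the agreement clause.

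The SAP does not support the stronger conclusion that agreement after allocation is the settled procedure, or that women will refuse in knowledge of their arm.

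The size and direction of any bias are unknown. On the assumed inputs above, the apparent relative risk under no effect runs from 0.75 (20% refusing, twice the risk) to 1.13 (20% refusing, half the risk), and is 1.00 if refusers have average risk. Rejection of a true null runs from 5% to about 14%. These figures show what could happen; they do not predict it. The calculation takes 207 per arm from Section 6 and leaves aside the 1:2 ratio stated under study methods, which is a separate matter.

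**What to change.** In the paragraph on randomization and initiation of the study:

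1. State that eligibility, signed consent and agreement to enter are recorded before the randomization software is opened.
2. Delete the condition of agreement that follows allocation, or move it ahead of the allocation step.
3. Limit data removal to women who decline before allocation.
4. State that every allocated woman keeps her study ID and is counted in her randomized arm in the primary analysis, with her data retained as far as her consent allows.
5. Report the number who refuse their arm after allocation, by arm.

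The same paragraph also moves control women who start metformin for gestational diabetes into the intervention group for analysis. That sentence will have to be reconciled with item 4.

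The cost is a few sentences and one required consent field in the randomization software. No sample-size figure changes. The downside is that a few women who refuse their arm stay in the denominator. The change is best made before enrollment, because records removed after allocation may not be recoverable at analysis.
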